***Non-parametric criteria***

Below are potential types of comparisons with relevant criteria:

1. To evaluate time changes in the parameters compared – Friedman test, nonparametric analogue of repeated measures analysis of variance.
2. For frequency analysis of contingency tables  $2 \times 2$  –  $\chi^2$  (if the frequency under comparison  $> 5$ ) or exact Fisher’s test (if one of the frequencies under comparison  $< 5$ ).

3. Cochran-Mantel-Haenszel test (modified  $\chi^2$  test for multiple comparisons) – to perform frequency analysis based on independent strata.
4. For frequency analysis of data on presence/absence of an event or outcome during repeated measurements (contingency tables with dependent strata) – survival analysis.

To perform the above-mentioned nonparametric statistical analysis the following SAS procedures are to be used:

- FREQ – Friedman test,  $\chi^2$  test and/or exact Fisher's test; Cochran-Mantel-Haenszel test.
- LIFETEST, PHREG – survival analysis.
- NPAR1WAY - Mann-Whitney test.

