***Statistical criteria***

All statistical calculations will be made using two groups of statistical criteria:

- parametric - to obtain effective estimates for random parameters in case the relevant conditions of method/model applicability are not violated (e.g. sphericity, normality, risk proportionality, etc.)
- nonparametric – in all other cases.

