***Parametric criteria***

The application of parametric criteria will be accompanied by a check of models for applicability (e.g. Kolmogorov-Smirnov test, Shapiro-Wilk test).

The following parameters and approaches are to be used:

1. To evaluate the differences in continuous variables obtained in one group at two different visits – Student’s test for matched samples.
2. To evaluate time changes in parameters compared - analysis of variance (ANOVA) or modified repeated measures covariance (ANCOVA).
3. In case of multiple comparisons of the groups various corrections for multiplicity will be used, e.g. Dunnett, Tukey, Scheffe, Holm adapted test, etc.
4. Generalized Linear Models and/or Mixed Linear Models will be used in case of abnormal data distribution.
5. Selection of the type of distribution, specification of factor and covariance structures of the model will be made using fit-statistics such as AIC (Akaike information criterion).

The following SAS software programs are supposed to be applied to the above listed tests and techniques:

- UNIVARIATE – normality verification of the distributions under comparison
- CORR, MEANS – calculation of descriptive statistics
- TTEST – Student’s test with all modifications
- GLM – generalized linear models for analysis of time changes (ANOVA, ANCOVA)
- GENMOD – generalized linear models
- MIXED – mixed linear models.

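### No between-arm analysis is assigned to the continuous change endpoints (MoCA, Barthel, SS-QOL), and Friedman, the numbered nonparametric method for change over time, cannot compare the arms

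*Combined protocol and SAP*

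**What the plan says.** Secondary endpoints 1, 3 and 4 are the week-24 changes in MoCA, Barthel index and SS-QOL total score. Endpoints 6 to 8 are the changes in the same scales from week 24 to week 28. No test is named beside any of them, and no later section links one to them.

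The plan does intend to compare arms. Evaluation of sample size, item 1.3, makes intergroup comparisons two-sided, and Data presentation promises confidence intervals for comparisons that support a conclusion.

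The method lists read as follows.

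- Statistical criteria: parametric methods apply while their conditions hold, with normality given as one example, and "nonparametric – in all other cases".
- Parametric criteria, item 1: the paired t-test serves "To evaluate the differences in continuous variables obtained in one group at two different visits".
- Parametric criteria, item 2: time changes are assessed by "analysis of variance (ANOVA) or modified repeated measures covariance (ANCOVA"). No arm factor, contrast or covariate is stated.
- Parametric criteria, item 4: "Generalized Linear Models and/or Mixed Linear Models will be used in case of abnormal data distribution".
- Parametric criteria, item 5: "Selection of the type of distribution, specification of factor and covariance structures of the model will be made using fit-statistics such as AIC".
- Non-parametric criteria, item 1: for time changes, the "Friedman test, nonparametric analogue of repeated measures analysis of variance". Items 2 to 4 concern frequencies and events.
- SAS procedure lists: "TTEST – Student’s test with all modifications" and "NPAR1WAY - Mann-Whitney test" appear without a stated comparison or endpoint.

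**The concern.** A placebo-controlled trial needs, for each endpoint on which it will draw a conclusion, a stated comparison of the two arms. Here the numbered tests for continuous change are a paired test within one group, an ANOVA/ANCOVA whose factors are left open, and Friedman. If the data are judged non-normal and the numbered nonparametric item is followed, the result says whether scores moved across visits. It does not say whether MMH-MAP differs from placebo.

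Subjects enter 3 to 6 months after a stroke with MoCA below 26. Both arms may therefore rise through recovery, practice on the test or regression to the mean. A significant Friedman or within-arm result could then be read as efficacy, and a real arm difference could go unseen. Leaving the analysis open also lets the method be settled after the data are known, and a baseline-adjusted analysis, which is more precise, may not be used.

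**Working it through.** **The plan's own figure.** The sample size concerns the binary primary endpoint. The unpooled fixed design needs (1.960 + 0.842)² × (0.6×0.4 + 0.4×0.6) / 0.2² = 94.19 per arm. The three-stage design in item 1.7 multiplies this by 1.1666: 94.19 × 1.1666 = 109.9, so 110. Then 110 / 0.8 = 137.5, so 138 per arm and 276 in total. The stated figures reproduce. They are used below only to set n = 110 per arm.

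**Why Friedman cannot compare arms.** With n subjects and k visits, the statistic (without ties) is 12 / [n k (k+1)] × Σ R_j² − 3n(k+1), where R_j is the sum over subjects of the within-subject rank at visit j. Arm does not enter. As a check, arm labels were shuffled 200 times in one simulated trial, and the pooled statistic stayed at 64.184 each time.

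**Simulation inputs.** The documents give no SDs or expected score gains, so these are assumptions: integer MoCA at baseline and weeks 8, 16 and 24; subject SD 2; error SD 1.5 per visit; visit means 0, 0.3, 0.6 and 0.8 in both arms; no missing data. Rounding adds 1/12 to the error variance, so the change SD is √[2 × (1.5² + 1/12)] = 2.16.

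**Friedman against a between-arm test (share of trials with p < 0.05).**

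| Scenario | Friedman, one arm | Friedman, pooled | Mann-Whitney on change |
|---|---|---|---|
| No drug effect, shared gain 0.8 | 90.4% | 99.7% | 4.9% |
| No drug effect, shared gain 0.4 | 32.2% | 60.4% | – |
| No drug effect, no true gain, entry cut MoCA < 26 (four settings) | 5.2–21.0% | 7.4–39.4% | 4.3–5.2% |
| True arm changes +0.4 and −0.4 | – | 5.2% | 76.1% |

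Other assumptions show the same behaviour. With continuous normal data, subject SD 0.8 and residual SD 0.6, a shared gain of 0.6 gives Friedman 100% and Mann-Whitney 5.5%. True arm changes of +0.2 and −0.2 give pooled Friedman 4.8% and Mann-Whitney 91.5%.

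**Does normality fail?** It depends on what is tested. Shapiro-Wilk on raw integer change fails in at least one arm in 98% of trials in the base case (60% at a change SD of about 2.85, 100% at about 1.5). On the residuals of a baseline-adjusted ANCOVA it fails in only 5–10% across the six SD settings tried.

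**A normality-driven choice.** Take Mann-Whitney if either arm fails, otherwise the t-test. With no drug effect, false positives are 4.8–5.0%, so type I error is not inflated.

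The cost is precision. The unadjusted SE of the week-24 difference is 2.16 × √(2/110) = 0.291. The correlation between two visits is 4 / (4 + 2.25 + 1/12) = 0.63, so baseline adjustment saves (1 − 0.63)/2 = 18% of the variance, and the SE becomes 0.291 × √0.816 = 0.263. For a 0.7-point effect, 0.7/0.263 − 1.96 = 0.70, which corresponds to about 76% power.

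| Subject SD / error SD | Normality-driven choice | Baseline-adjusted ANCOVA |
|---|---|---|
| 2 / 1.5 | 64.8% | 75.3% |
| 2 / 2 | 44.4% | 56.2% |
| 1.5 / 1.5 | 65.2% | 79.3% |
| 3 / 1.5 | 65.3% | 71.1% |
| 2 / 1 | 93.2% | 96.4% |
| 3 / 1 | 92.2% | 94.6% |
| 3 / 1.5, entry cut MoCA < 26 | 66.6% | 71.2% |

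**The case against.** The strongest reply is that the tools are all there. Mann-Whitney compares two independent samples, so in a two-arm trial its natural use is arm against arm. Item 3 of Parametric criteria speaks of corrections when groups are compared, and item 2 may take an arm factor for granted. This stands in part: the gap is one of assignment, not absence. It does not close the gap. The Non-parametric section presents its SAS list as carrying out the analyses named before it, yet Mann-Whitney is not among them. An implied arm factor in item 2 would still leave the contrast, the baseline adjustment and the choice between two models open. Item 5 need not mean that AIC could drop the arm term, but it does leave distribution and factor structure to the data.

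A second reply is that the two rules for non-normal data can partly be reconciled. A generalized linear model with a suitable distribution has not failed its own conditions, so item 4 may be the parametric route, with nonparametric methods kept for cases where no model applies. That is a fair reading. The mixed linear model in item 4 remains unexplained, and nothing says which route comes first. The instructions are unreconciled; they are not flatly contradictory.

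Third, a reader might infer from the 98% that MoCA is almost bound to fall into the non-normal branch. The documents do not support that. Parametric criteria speaks both of checking the model and, in the UNIVARIATE line, of the distributions compared. The first reading points to residuals, where failure is uncommon.

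Fourth, the Friedman percentages and the 65% against 75% might be taken as error rates or power of this plan. They are not. No section pools the arms under Friedman or rests an efficacy claim on it. The choice between t-test and Mann-Whitney was constructed for illustration, and ANCOVA is itself a named method.

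**Conclusion.** The point holds as a pre-specification gap on the continuous secondary endpoints 1, 3 and 4, and likewise 6 to 8. No between-arm test, contrast or effect measure is assigned to them, and the numbered nonparametric method for change over time cannot supply one. That conclusion follows from the text and the form of the Friedman statistic, and needs no assumed figures.

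The size is illustrative only. It rests on assumed SDs, means and gains and on complete data, although the plan expects at least 20% withdrawal. Across the settings tried, an unadjusted, normality-driven choice has about 2 to 14 percentage points less power than baseline-adjusted ANCOVA for a 0.7-point effect (94.6 − 92.2 = 2.4; 79.3 − 65.2 = 14.1).

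Two stronger readings should be set aside. The binary primary endpoint is not affected, because its analysis does not pass through these methods. The normality check does not raise the false-positive rate. The plan should be changed, but the defect does not threaten the trial's main conclusion. Confidence is high for the missing assignment and lower for its magnitude.

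**What to change.** For endpoints 1, 3 and 4, replace the normality-driven choice of method with one pre-specified baseline-adjusted comparison of the arms. For example, use PROC MIXED on change from baseline at weeks 8, 16 and 24, with arm, visit, arm-by-visit and baseline score, and report the week-24 arm difference with its 95% CI. A week-24 ANCOVA is an acceptable simpler form, but it does not use the week 8 and 16 scores of subjects who leave early.

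In addition:

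- name Mann-Whitney on week-24 change as the sensitivity analysis;
- limit AIC to the choice of covariance structure;
- keep Friedman and the paired t-test as within-arm description only;
- apply the same baseline-adjusted approach to endpoints 6 to 8;
- reconcile the Statistical criteria section with item 4 of Parametric criteria.

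The cost is SAP wording and a little more analysis work. The visits, scores and SAS procedures are already planned, and no new data are needed.

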### **Interim analysis**

Two interim analyses are scheduled in the study: involving 15% and 30% subjects recruited. Type 1 error distribution is in accordance with O'Brien-Fleming alpha spending function, type II - according to Pocock test. Early study termination is possible both due to acceptance and rejection of null hypothesis.

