### ***Evaluation of sample size***

The sample size was assessed in accordance with the following rules and assumptions:

1. Statistical assumptions
  - 1.1 the power of statistical tests ' $P = (1 - \beta)$ ' is 80% (the probability of correct rejection of the null hypothesis is 0.8)
  - 1.2 the probability of type 1 error 'a' is less than 5% (the probability of false acceptance of the alternative hypothesis is less than 0.05);
  - 1.3 statistical criteria of intergroup comparisons will be two-sided, equivalence criterion - one-sided;

---

 Holder of license: OOO "NPF "Materia Medica Holding", No. 70100045.

- 1.4 calculation of sample size will be based on the assumptions on the expected effect declared in the primary efficacy criterion of the protocol;
- 1.5 ratio between sample sizes of MMH-MAP and Placebo sample sizes is 1:1 (1 MMH-MAP subject per 1 Placebo subject);
- 1.6 statistical hypotheses - null and alternative hypotheses on the difference between test product and placebo under the dosing regimen used:

$$H_0: \Theta_1 - \Theta_2 = 0$$

$$H_a: \Theta_1 - \Theta_2 \neq 0$$

where  $\Theta_1$  is frequency of the claimed event in MMH-MAP group, a  $\Theta_2$  is frequency of the claimed event in Placebo group;

- 1.7 calculation of sample size for statistical criteria was made using the following program code:

```
Proc seqdesign errspend
```

```
Design nstages = 3
```

```
Info = cum (0.15,0.3,1)
```

```
Method (alpha) = UNI (rho = 0.5 tau = 0)
```

```
Method (beta) = UNI (rho = 0 tau = 0)
```

```
Stop = both
```

```
Alpha = 0.05
```

```
Beta = 0.2
```

```
Samplesize model = twosamplefreq (test = PROP nullprop = 0.4 prop = 0.6)
```

```
Run;
```

- 1.8 terminal sample size will be determined using the formula:

$$N_T = N_{PP} / (1 - R_w)$$

where  $N_T$  – terminal sample size;  $N_{PP}$  – result of calculation in c. 1.7 i.e.

scheduled number of subjects completing the study per protocol;  $R_w$  – withdrawal rate.

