### ***Data presentation***

Descriptive statistics will be provided for each study continuous / interval variable. Numerical data will be presented by mean, standard deviation, min and max values. Comparisons suggesting statistical conclusion will have the relevant confidence intervals. Outliers will be analyzed individually. The data will be grouped by visits. The categorical variables will be presented as frequency tables by visits.

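### No test is assigned to the primary responder endpoint, and baseline MoCA, measured on everyone, is not named as a covariate or stratum; pre-specified adjustment would be a cheap improvement if it predicts response

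*Combined protocol and SAP*

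**What the plan says.** The Primary endpoint section defines response as a MoCA gain of at least 1 point over baseline after 24 weeks. Under Evaluation of sample size, item 1.6 sets the hypothesis as a difference between two frequencies, the first of which "is frequency of the claimed event in MMH-MAP group". Item 1.7 sizes the trial with "Samplesize model = twosamplefreq (test = PROP nullprop = 0.4 prop = 0.6", an unadjusted comparison.

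The statistical sections are organised by data type, not by endpoint. Non-parametric criteria opens with "Below are potential types of comparisons with relevant criteria". Several of its items could be applied to responder data:

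- Item 2 gives chi-square or Fisher "For frequency analysis of contingency tables" of size 2×2.
- Item 3 gives Cochran-Mantel-Haenszel "to perform frequency analysis based on independent strata", with no stratum named.
- Item 4 gives survival analysis for events recorded over repeated visits.

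The Parametric criteria section adds "GENMOD – generalized linear models" without an endpoint or covariate, and its item 5 leaves factor specification to fit statistics.

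Baseline MoCA is an eligibility measure (Inclusion criteria, item 3) and is scheduled at Visit 1 (Schedule of study procedures). It is not named as a covariate or stratum anywhere.

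Two other statements bear on the choice. Data presentation says "Comparisons suggesting statistical conclusion will have the relevant confidence intervals". Interim analysis says "Two interim analyses are scheduled in the study: involving 15% and 30% subjects recruited", and the trial may stop early in either direction.

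**The concern.** The natural reading is an unadjusted chi-square test. The plan does not say so, and it does not say whether baseline MoCA enters the comparison. Two things follow.

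First, a possible gain in precision is not secured. Regression to the mean would make low baseline scorers more likely to gain a point, so baseline may predict response. True recovery that rises with the baseline score could cancel or reverse that pattern. If an association exists in either direction, a pre-specified adjustment raises power at no cost in patients. Reduced sensitivity to chance baseline imbalance is the same gain seen another way, not an additional one.

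Second, with several candidate tests open, the statistic to be compared with the stopping boundaries is not fixed before the first look.

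**Working it through.** **1. Inputs.** From Evaluation of sample size: 60% versus 40% response, 1:1 allocation, two-sided alpha 0.05, beta 0.2, information fractions 0.15 / 0.30 / 1, O'Brien-Fleming-shaped alpha and Pocock-shaped beta boundaries, stopping for either, 20% withdrawal. The documents give no R² between baseline MoCA and response, and no baseline mean, SD or reliability. All of these are assumptions below.

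**2. The plan's own figure.** Solving the three-stage design gives rejection at |Z| ≥ 4.84, 3.42, 1.874 and acceptance at |Z| < 0.02, 0.51, 1.874, with required drift 3.026.

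- n per group = 3.026² × (0.6×0.4 + 0.4×0.6) / 0.2² = 9.157 × 0.48 / 0.04 = 109.9, so 110.
- 110 / 0.8 = 137.5, so 138 per group and 276 in total.
- At 110 per group the drift is 0.2 / √(0.48/110) = 3.028, and power is 80.0%.

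The stated sample size is reproduced.

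**3. Adjustment, by integration.** Adjusting divides the drift by √(1−R²). The last row is 220/(1−R²) − 220, the extra completers an unadjusted analysis would need for the same precision.

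| Assumed R² | 0 | 0.01 | 0.02 | 0.04 | 0.06 | 0.10 |
|---|---|---|---|---|---|---|
| Power, % | 80.0 | 80.3 | 80.7 | 81.4 | 82.1 | 83.5 |
| Gain, points | 0 | 0.35 | 0.7 | 1.4 | 2.1 | 3.5 |
| Completers | 0 | 2 | 4 | 9 | 14 | 24 |

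**4. Adjustment, by simulation of the rule proposed in the fix.** Each scenario used 100,000 trials with looks at 33, 66 and 220 completers, taking 15% and 30% to mean fractions of 220. Baseline was integer MoCA truncated below 26. Monte Carlo SE of power is 0.13 points.

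| Scenario (assumed mean / SD / reliability) | R² | Chi-square, % | Proposed rule, % | Difference | Net of 0.6 |
|---|---|---|---|---|---|
| Response independent of baseline | 0 | 78.9 | 79.5 | 0.6 | 0 |
| 23 / 3 / 0.8, recovery cancels regression to the mean | 0.0001 | 78.7 | 79.2 | 0.5 | about 0 |
| 23 / 3 / 0.9 | 0.02 | 78.8 | 80.2 | 1.4 | 0.8 |
| 23 / 3 / 0.9, recovery reverses the direction | 0.03 | 78.8 | 80.7 | 1.9 | 1.3 |
| 23 / 3 / 0.7 | 0.06 | 78.8 | 81.8 | 3.0 | 2.4 |
| 25 / 4 / 0.5 | 0.07 | 78.9 | 82.0 | 3.1 | 2.5 |

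Differences are taken from rounded figures, so the last digit can move by 0.1. The 0.6 points at R² = 0 cannot come from baseline. They are attributed to the coarse 2×2 statistic at the second look: with 33 per arm, a difference of two responders gives Z = (2/33) / √(0.25×2/33) = 0.49, just inside the 0.51 acceptance bound. They are subtracted from the claimed gain.

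**5. Type I error.** Over 12 null scenarios (both arms at 40% or both at 50%, Monte Carlo SE 0.07 points):

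- unadjusted chi-square: 5.0–5.5%, mean 5.25%
- proposed rule: 5.1–5.4%, mean 5.23%
- adjusted at every look without the small-sample correction: 5.2–5.6%, mean 5.39%

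With the correction, the gain is not bought with extra type I error relative to chi-square.

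**6. Cost of leaving the choice open.** In a single-look simulation at 110 per arm with 40% response in both arms, taking the best of chi-square, logistic and stratified Cochran-Mantel-Haenszel gave type I error of about 5.8%, 6.6% and 7.9% at baseline odds ratios of 1.0, 1.65 and 2.72 per SD. Each test alone stayed between 4.9% and 5.5%. This is what an open choice could cost, not evidence that the sponsor would choose in this way.

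**The case against.** The strongest reply is that nothing is broken. An unadjusted comparison of proportions is legitimate, matches the stated hypothesis and the sample-size code, and is adequately powered. Baseline already enters through the definition of response. All of that stands, and it is why this is offered as an improvement and not as a correction.

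The gain rests on an assumed R². This also stands. Two of the six simulated scenarios give no gain, the largest needs a reliability of 0.5, and the 3.5 points at R² 0.10 come from integration only, since no simulated scenario exceeds 0.07.

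The document describes itself as a protocol summary, so a fuller plan may assign the test. That is possible, but the text available does not.

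A simpler remedy is already on the plan's list: Cochran-Mantel-Haenszel with baseline strata named, used at all looks. With three strata and log-odds of 0 / 0.3 / 0.5 per SD, its simulated power was 78.3 / 79.1 / 80.0% against 78.7% for chi-square throughout, with type I error of 5.0–5.1% against 5.2–5.5%. A separate simulation of the logistic rule at the same log-odds gave 79.2 / 79.8 / 81.4% against 78.7 / 78.4 / 78.7% for chi-square. Stratification is therefore a reasonable fallback with slightly tighter type I control, but it recovers less of the gain and costs about 0.4 points if baseline is not prognostic.

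Finally, item 1.2 of the sample-size section asks for type I error below 5%, and the proposed rule's simulated range is 5.1–5.4%. The unadjusted chi-square also exceeds 5% in the same scenarios, reaching 5.5%, so this does not favour leaving the plan as it is. The choice of analysis set and the handling of missing Week 24 scores are separate questions that this point does not settle.

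**Conclusion.** The point holds as an optional improvement, with medium confidence. No test is tied to the primary endpoint, and baseline MoCA is available but unused as a covariate or stratum. There is no error and no power shortfall: the likely unadjusted test is valid, and 110 per group is adequate under the plan's own rates. The benefit of adjustment is modest and conditional. It is nil if baseline does not predict response, and about 0.8 to 2.5 points net in the simulated scenarios with R² of 0.02 to 0.07. This rests on the plan's 60% and 40% rates, looks at 33, 66 and 220 completers, and assumed baseline distributions. Fixing one statistic before the first look is worthwhile whatever R² turns out to be.

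**What to change.** Add one SAP paragraph, written before the first interim look:

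- **Primary analysis:** logistic regression of Week 24 response on treatment and continuous baseline MoCA. Report the standardised (marginal) risk difference with a 95% confidence interval. This keeps the difference in frequencies of item 1.6 as the effect measure.
- **Variance:** influence-function variance multiplied by n/(n−3).
- **First look (about 33 completers):** unadjusted Pearson chi-square only.
- **Second look and final:** the standardised difference divided by its corrected SE, compared with the sequential boundaries.
- **Sensitivity analysis:** unadjusted chi-square.
- **Check:** confirm the type I error of this rule by simulation before unblinding.

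The cost is the paragraph, slightly more programming and one simulation, with no new data, visits or patients. The downside is a possible slight excess in type I error, up to 5.4% with the correction and 5.6% without it, against up to 5.5% for chi-square. If the sponsor prefers something simpler, the minimum is one sentence naming the primary test and saying whether baseline MoCA enters it; Cochran-Mantel-Haenszel with pre-set MoCA strata would serve, with a smaller gain.
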